5.4 Level of Significance, Multiple Comparisons and Multiplicity

For all significance tests, exact p-values (to four decimal places) will be calculated and quoted.

[figure not shown]
There are two dose regimens and one primary efficacy parameter, and three key secondary efficacy parameters, which are intended to support conclusions based on the primary parameter. For these analyses type-1 error rate will be controlled as described below. In addition, sensitivity analyses and several other endpoints will be considered as supportive and descriptive, and no adjustments for multiplicity will be made for these analyses.

Two sets of comparisons (for the primary and key secondary endpoints) will be carried out. The first will be of once daily dosing vs. placebo, and the second will be of intermittent dosing vs. placebo. In order to account for multiplicity, an overall hierarchical testing procedure will be applied in the steps between primary and secondary endpoints, while a Hochberg procedure will be applied among the secondary endpoints. An overall significance level of 0.05 will be applied.

The first step will be the test of once daily dosing vs. placebo for the primary endpoint. If the null hypothesis is rejected, then once daily dosing vs. placebo will be tested for the three key secondary endpoints using a Truncated Hochberg procedure (applying a truncation factor of 0.75). If at least one null hypothesis is rejected among the key secondary endpoints, then the hierarchical testing will proceed with comparing intermittent dosing vs. placebo for the primary endpoint based on a significance level depending on the number of successes in previous step, as applicable to the truncation factor used. Last, if the null hypothesis is rejected for the comparison of primary endpoint in intermittent dosing vs placebo, then the key secondary endpoints will be compared for intermittent dosing vs placebo using the regular Hochberg and based on an overall significance level corresponding to the previous step. The truncated Hochberg procedure using a truncation factor of 0.75 among the tests in the family of secondary tests between Molgramostim OD and Placebo, implies ordered alpha levels of 0.0417, 0.0229, 0.0167, while preserving alpha 0.05 for the first test between Molgramostim Int. and Placebo if all null hypotheses are rejected, and 0.0083 and 0.0042 if only two or one of the ordered hypotheses are rejected, respectively. The steps of the testing procedure applied to account for multiple testing among the primary and key secondary endpoints are illustrated in figure 2.

All of the analyses will be tabulated separately (irrespective of statistical significance), although an overview of the results of the steps in the testing procedure will be also tabulated.

Figure 2 Overview of Analyses for Primary and Key secondary endpoints

Results from analyses denoted “Main analysis” will be part of testing procedures where adjustments to control for multiple testing will be implemented.

MI – Multiple imputation,

5.5 Adjustment for Covariates

In all analyses of ‘change from baseline’, the corresponding baseline value of the parameter being analysed will be included in an analysis of covariance (ANCOVA) model. The WLL (stratification) will be included in all analysis models. For endpoints analysed by a mixed model for repeated measurements (MMRM), baseline will be included as a covariate in the model. Geographical region (as defined for subgroups), unique country or centre will not be adjusted for in the statistical analyses, instead adjustment will be made for Japan vs all other countries in all parametric analyses.

5.6 Handling of Dropouts and Missing Data

Different approaches will be applied for evaluation of impact of missing data on the results for primary and key secondary endpoints, each is described in previous sections.

5.7 Multicentre Studies

Summary statistics will be presented for the whole population. For baseline demographics and disease characteristics, primary endpoint, and key secondary endpoints, summary statistics will also be presented by geographical region. The results for the primary and key secondary endpoints will be presented graphically as well as in tables. Centre will not be included as a stratification factor in either the randomisation procedure or data analysis. All subject listings will be sorted by centre.

5.8 Examination of Subgroups

For the primary endpoint, key secondary efficacy endpoints, and AEs summary statistics will be presented by subgroups. In addition to subgroups by region, as stated in protocol, summary statistics of observed data, during the double-blind treatment period, will be prepared for subgroups defined by age, sex, aPAP severity, aPAP duration since diagnosis and WLL conducted previously, for the assessments as described in Table 2.

Table 2: Subgroup Analyses

	Age Groups	Sex	aPAP severity	aPAP diagnosis	Previous WLL
	</≥ 65	M/F	DSS 2/3/4/5	</≥ 6m	Y/N
Subject Disposition	+	+	+	+	+
Exposure	+	+	+	+	+
Efficacy					
(A-a)DO2	+	+	+	+	+
6MWD	+	+	+	+	+
SGRQ total score	+	+	+	+	+
Time to WLL	+	+	+	+	+
FVC			+		
DLCO			+		
KL-6			+		
Safety					
AEs (SOC/PT)	+	+			

Furthermore, estimated differences with corresponding 95% CIs will be presented for the efficacy endpoints split by the subgroups in forest plots. The estimated differences and the 95% CIs will be calculated by applying the general ANCOVA.

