- ANCOVA based on the per protocol set (PPS).

Mean profiles for 6MWD and SGRQ over time will be provided.

Time to WLL during 24-weeks treatment

Kaplan-Meier plots will be used to assess time to WLL (time from randomisation to documentation of fulfilment of criterion for requiring WLL) and treatment comparisons corresponding to those made for primary endpoint, will be analysed by a logrank test adjusting for the randomisation strata (WLL). Subjects who fulfil the criteria for rescue treatment (i.e., worsening of aPAP based on symptoms, reduced exercise capacity and/or findings of hypoxemia or desaturation according to the Investigator's judgement), will be counted as if WLL was conducted at the date of fulfilment of rescue treatment criteria. In this analysis, subjects withdrawing from the trial will be handled as censored at time of discontinuation, and subjects who reach week 24 and have not needed WLL will be censored at time point for Visit at week 24. Survival estimates for time to WLL will be tabulated for subjects in each group who require WLL, by relevant time points, along with 95% Cis.

Sensitivity analyses for time to WLL will be carried out as follows:

- Any subject withdrawing from trial before week 24 and before fulfilling criteria for WLL will be handled as having WLL the day after discontinuation date. This is done to

evaluate the impact of missing data and censoring due to withdrawals. The same analyses as planned above will be conducted in order to evaluate the robustness of results with regards to the handling of censoring.

- A Cox regression will be applied where the hazard ratio and its 95% confidence interval will be estimated, while including adjustment for treatment, Japan vs other countries and WLL (stratification). The analysis will be done using the same approach for handling censoring as done in the main analysis.

Further Secondary Efficacy Analyses

The further secondary efficacy endpoints will be statistically analysed, although the analyses will be considered supportive rather than confirmatory, and will therefore not be part of the testing procedures implemented for primary and key secondary efficacy endpoints to control for multiplicity.

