Figure	14.2.2.36	Forest Plot for analyses of change from baseline in SGRQ total score, Molgramostim Int. vs Placebo by subgroups		X					
Table	14.2.2.37	Summary of number of subjects in need of WLL during 24-weeks of treatment		X	X				
Table	14.2.2.38	Life table summary of time from randomization to need of WLL		X					
Figure	14.2.2.39	Kaplan – Meier plot for time to need of WLL during 24-weeks of treatment		X					
Table	14.2.2.40	Analysis of difference between treatment groups (logrank test) in time to WLL during 24 weeks of treatment		X					
Table	14.2.2.41	Sensitivity analysis of difference between treatment groups (Cox regression) in time to WLL during 24 weeks of treatment		X					
Table	14.2.2.42	Sensitivity analysis of difference between treatment groups (logrank test) in time to WLL during 24 weeks of treatment – alternative censoring		X					
Table	14.2.2.43	Sensitivity analysis of difference between treatment groups (logrank test) in time to WLL during 24 weeks of treatment			X				
Table	14.2.2.44	Summary of number of subjects in need of WLL during 24-weeks of treatment by Age Group		X					
Table	14.2.2.45	Summary of number of subjects in need of WLL during 24-weeks of treatment by Sex		X					
Table	14.2.2.46	Summary of number of subjects in need of WLL during 24-weeks of treatment by aPAP severity		X					
Table	14.2.2.47	Summary of number of subjects in need of WLL during 24-weeks of treatment by aPAP diagnosis		X					
Table	14.2.2.48	Summary of number of subjects in need of WLL during 24-weeks of treatment by strata and by visit		X					
Figure	14.2.2.49	Kaplan – Meier plot for time to need of WLL during 24-weeks of treatment by strata		X					
Table	14.2.2.50	Summary of number of subjects in need of WLL during 24-weeks of treatment by region		X					
Figure	14.2.2.51	Kaplan – Meier plot for time to need of WLL during 24-weeks of treatment by region		X					
Figure	14.2.2.52	Forest Plot for analyses of time to WLL , Molgramostim OD vs Placebo by subgroups		X					
Figure	14.2.2.53	Forest Plot for analyses of time to WLL, Molgramostim Int. vs Placebo by subgroups		X					
Table	14.2.2.54	Overview of statistical hypothesis testing for primary and key secondary efficacy endpoints according to testing procedure		X					
Further Secondary Efficacy Endpoints									
Table	14.2.3.1	Summary of VC (% predicted) and change from baseline in VC (% predicted) by visit during 24 weeks treatment		X					

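### SAP 5.8 prescribes ANCOVA for every efficacy forest plot and makes no exception for time to WLL, a censored endpoint that SAP 5.3.7 analyses by logrank and Cox

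*SAP*

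**What the plan says.** SAP 5.8 (Examination of Subgroups) states that "estimated differences with corresponding 95% CIs will be presented for the efficacy endpoints split by the subgroups in forest plots", and then that "The estimated differences and the 95% CIs will be calculated by applying the general ANCOVA". No endpoint is excepted. Table 2 in the same section lists time to WLL under Efficacy and marks it for all five subgroup factors.

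Appendix 1, section 14.2, lists the two outputs: Figure 14.2.2.52, "Forest Plot for analyses of time to WLL , Molgramostim OD vs Placebo by subgroups", and Figure 14.2.2.53, "Forest Plot for analyses of time to WLL, Molgramostim Int. vs Placebo by subgroups". Neither title names a method.

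SAP 5.3.7 handles the same endpoint as time-to-event data. It plans Kaplan-Meier plots and a logrank test adjusted for the randomisation strata. On censoring it says that "subjects withdrawing from the trial will be handled as censored at time of discontinuation" and that "subjects who reach week 24 and have not needed WLL will be censored at time point for Visit at week 24". As a sensitivity analysis, "A Cox regression will be applied where the hazard ratio and its 95% confidence interval will be estimated", with terms for treatment, Japan versus other countries and the WLL stratum. Nothing extends that Cox model to the subgroups.

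SAP 5.5 describes the ANCOVA as the model for change-from-baseline analyses, with the baseline value of the analysed parameter as a covariate.

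**The concern.** The method stated for the two time-to-WLL forest plots does not suit the data. ANCOVA has no place for a censoring indicator. A subject censored at Week 24 would enter as if WLL had occurred at Week 24, and a subject who withdrew at Week 8 as if WLL had occurred at Week 8. The baseline covariate that SAP 5.5 requires does not exist for this endpoint.

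Subgroup forest plots are read for consistency of effect. Time to WLL is a key secondary endpoint, and Protocol 5.2 presents the need for WLL as an important clinical outcome. If the sentence is followed literally, the plotted estimates mix time to WLL with length of follow-up. If it is not followed, someone has to choose another method, and a choice made after unblinding would be post hoc.

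**Working it through.** The plan gives no figure for these plots, so there is nothing to reproduce. The check has three parts.

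**1. The text.**

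| Place | What it fixes for time to WLL |
|---|---|
| SAP 5.8, text | Forest plots for the efficacy endpoints, by ANCOVA |
| SAP 5.8, Table 2 | Time to WLL is an efficacy row, all five factors |
| SAP Appendix 1, Figures 14.2.2.52 and 14.2.2.53 | The plots are planned; no method named |
| SAP 5.3.7 | Censored data: Kaplan-Meier, logrank, Cox (whole population) |
| SAP 5.5 | ANCOVA carries the parameter's baseline value |

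The first three rows together assign ANCOVA to time to WLL. The last two are incompatible with that.

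**2. How much censoring.** Inputs are from SAP Appendix 2, section 1.3, and SAP 3.2.

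- Planning rates at 24 weeks are 5% on active and 20% on placebo. With 1:1:1 allocation, the pooled event rate is (5% + 5% + 20%)/3 = 10%, so about 90% of times are censored. In 135 subjects that is 13.5 events.
- The blinded re-estimation count was 4 of 78. Here 4/78 = 5.1%, so about 95% were event-free. Scaled to 135 subjects, 135 × 4/78 = 6.9 events. Follow-up of the 78 was incomplete, and Appendix 2 itself calls the rate probably slightly underestimated.

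**3. What a mean difference in recorded time estimates.** Take exponential event times with probability p of WLL by Week 24, and exponential dropout with probability d by Week 24. The hazard ratio at the planning rates is ln(0.95)/ln(0.80) = 0.0513/0.2231 = 0.230. The mean recorded time, in weeks, is

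m(p, d) = 24 × (1 − (1−p)(1−d)) / (−ln((1−p)(1−d))).

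With d = 0 this is the 24-week restricted mean:

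- active: 24 × 0.05/0.0513 = 23.39
- placebo: 24 × 0.20/0.2231 = 21.51
- difference: 1.88 weeks

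The documents give no dropout rate, so d was varied from 0% to 30% per arm as an assumption. The simulation used 20,000 subjects per arm. Its linear-model column is the unadjusted mean difference; baseline covariates unrelated to treatment would not change what it estimates.

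| Dropout, active/placebo | Formula: active − placebo (weeks) | Simulated difference (weeks) | Simulated Cox hazard ratio |
|---|---|---|---|
| 0%/0% | 23.39 − 21.51 = 1.88 | 1.85 | 0.24 |
| 20%/20% | 20.99 − 19.36 = 1.63 | 1.61 | 0.23 |
| 20%/5% | 20.99 − 20.99 = 0.00 | 0.01 | 0.23 |
| 5%/20% | 22.81 − 19.36 = 3.45 | 3.45 | 0.24 |
| 30%/0% | 19.71 − 21.51 = −1.80 | −1.80 | 0.23 |
| No true effect (20% events in both arms), 20%/5% | 19.36 − 20.99 = −1.63 | −1.67 | 1.02 |

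In the 20%/5% row the effect disappears exactly, because 0.95 × 0.80 = 0.80 × 0.95: the linear model cannot tell a withdrawal from a WLL. The Cox estimate stays close to the true 0.230, or to 1 when there is no effect.

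**4. Sparse cells.** At a 5% active rate, the chance that an active arm has no event in a subgroup is 0.95ⁿ: about 10% for n = 45, 32% for n = 22 and 57% for n = 11. Only 45 is the planned arm size; 22 and 11 are assumed cell sizes, roughly a half and a quarter of an arm. The severity factor has four levels, so cells of that order are plausible.

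**The case against.** The strongest reply is that the sentence was written for the continuous endpoints. SAP 5.5 ties ANCOVA to change from baseline, and the phrase about estimated differences fits those endpoints. Appendix 1 titles the other forest plots as change from baseline and the WLL plots as analyses of time to WLL. The drafting of 5.8 is loose elsewhere too: KL-6 is an efficacy row of Table 2 but has no forest plot in Appendix 1. This is probably how the sentence arose. It still leaves ANCOVA as the only method stated for the two figures, because no other section supplies one.

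The consequence is also small. SAP 5.4 keeps supportive analyses outside the multiplicity procedure, and Protocol 12.1.3 plans no interaction tests for subgroups. Appendix 1 already provides counts of subjects needing WLL by age, sex, severity, time since diagnosis, stratum and region, and Kaplan-Meier plots by stratum and region. All of that stands and limits the weight of the point.

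A reader might go further and infer that the plotted differences would be meaningless, or would estimate no treatment effect at all. The documents do not support that. Without withdrawals the difference approximates a restricted mean difference, and with equal 20% dropout it is attenuated (1.63 against 1.88 weeks) but still reflects an effect. Disappearance or reversal needs unequal dropout, which is an assumption here. Protocol 12.1.5 expects subjects to be retained and little (A-a)DO₂ data to be missing at Week 24.

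Nor should 95% be taken as the final censoring proportion. It comes from subjects with incomplete follow-up: only 51 had a Week 24 result for SGRQ or 6MWD, against 78 in the WLL count.

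**Conclusion.** The point holds as an unstated exception. SAP 5.8 prescribes ANCOVA for all efficacy forest plots, and this is the wrong method for time to WLL by the SAP's own treatment of that endpoint in 5.3.7 and its own definition of the ANCOVA in 5.5.

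Most recorded times will be censoring times, about 90% at the planning rates. At those rates, and with assumed dropout of 0% to 30% per arm, the ANCOVA difference could lie anywhere from about −1.8 to +3.4 weeks around a true restricted mean difference of 1.88 weeks. The size of any distortion in this trial cannot be derived from the documents, because it depends on dropout by arm.

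The effect is confined to Figures 14.2.2.52 and 14.2.2.53. A reader might infer that the confirmatory result for time to WLL is at risk. It is not: the logrank test and the testing procedure in SAP 5.4 do not use these plots.

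**What to change.** In SAP 5.8:

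- Restrict the ANCOVA sentence to the continuous change-from-baseline endpoints.
- For time to WLL, plot the Cox hazard ratio with its 95% CI by subgroup, using the 5.3.7 model (treatment, Japan versus other countries, WLL stratum) and the 5.3.7 censoring rules. Reduce the model to treatment only where events are sparse.
- State a minimum number of events, fixed before unblinding. Below it, or where either arm has no event, show event counts only. A rule for zero events alone is not enough, because one or two events cannot support a three-term Cox model.

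The cost is a few sentences in one section and no new data. The downside is that some subgroup rows will show counts and no estimate. With about 7 to 14 events expected across three arms, that may be a sizeable share of the rows.

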5.9 Interim Analysis

Analyses will be conducted when all subjects have completed the double-blind treatment period, before all subjects have completed the open-label follow-up period. This does not constitute a statistical interim analysis.

5.10 Data Monitoring

An independent DSMB comprised of pulmonologists from lung centres who are experts in interstitial lung disease, and in conducting clinical studies were appointed and assigned for safety surveillance of the trial. The DSMB members were not investigators in the study. All members of the DSMB were unblinded to the treatment received by the subject and the subject identification.

All study team members remained blinded. Unblinded safety and tolerability data listings for the DSMB review were provided by a statistician from TFS who is independent of the study.

All details of the procedures related to independent unblinding, delivery and review of data are described in the DSMB Charter, V4.0, dated 18 Sep 2018.

14.1 DEMOGRAPHIC DATA									
Table	14.1.1	Subject Disposition Analysis Sets and Reason for Exclusions	X						X
Table	14.1.2	Subject Disposition Analysis Sets and Reason for Exclusions by Age Group	X						
Table	14.1.3	Subject Disposition Analysis Sets and Reason for Exclusions by Sex	X						
Table	14.1.4	Subject Disposition Analysis Sets and Reason for Exclusions by aPAP severity	X						
Table	14.1.5	Subject Disposition Analysis Sets and Reason for Exclusions by aPAP diagnosis	X						
Table	14.1.6	Subject Disposition Analysis Sets and Reason for Exclusions by previous WLL	X						
Table	14.1.7	Subject Discontinuation		X	X	X	X	X	X
Table	14.1.8	Number of Subjects by Visit		X	X	X	X	X	X
Table	14.1.9	Demographics: Age Sex and Race		X	X	X	X	X	X
Table	14.1.10	Demographics: Age Sex and Race by Region		X	X	X			
Table	14.1.11	Demographics: Weight Height and BMI		X	X	X	X	X	X
Table	14.1.12	Demographics: Weight Height and BMI by Region		X	X	X			
Table	14.1.13	aPAP history		X	X	X	X	X	X
Table	14.1.14	aPAP history by Region		X	X	X			
Table	14.1.15	Medical history		X	X	X	X	X	X

			SCR	DB-FAS	DB-PPS	DB-SAF	FU-FAS	FU-MOL INT	FU-SAF
14.2 EFFICACY DATA									
Primary Endpoint									
Table	14.2.1.1	Summary of (A-a)DO2 and change from baseline in (A-a)DO2 by visit during 24 weeks treatment		X	X				
Figure	14.2.1.2	Mean profiles of (A-a)DO2 over time		X					
Figure	14.2.1.3	Mean change profiles of (A-a)DO2 over time		X					
Table	14.2.1.4	Summary of (A-a)DO2 and change from baseline in (A-a)DO2 while on treatment by visit during 24 weeks treatment		X					
Table	14.2.1.5	Analysis of primary endpoint change from baseline in (A-a)DO2 after 24 weeks (ANCOVA)		X					
Table	14.2.1.6	Sensitivity analysis for primary endpoint change from baseline in (A-a)DO2 after 24 weeks (MMRM)		X					
Table	14.2.1.7	Sensitivity analysis for primary endpoint change from baseline in (A-a)DO2 after 24 weeks (ANCOVA) multiple imputation analysis		X					
Table	14.2.1.8	Sensitivity analysis for primary endpoint change from baseline in (A-a)DO2 after 24 weeks (ANCOVA) multiple imputation of measurements following WLL		X					
Table	14.2.1.9	Sensitivity analysis for primary endpoint change from baseline in (A-a)DO2 after 24 weeks (ANCOVA) tipping point analysis		X					
Table	14.2.1.10	Sensitivity analysis for primary endpoint change from baseline in (A-a)DO2 after 24 weeks (ANCOVA) worst case analysis		X					
Table	14.2.1.11	Sensitivity analysis for primary endpoint change from baseline in (A-a)DO2 after 24 weeks (ANCOVA) completer analysis		X					
Table	14.2.1.12	Sensitivity analysis for primary endpoint change from baseline in (A-a)DO2 after 24 weeks (ANCOVA)			X				
Table	14.2.1.13	Summary of (A-a)DO2 and change from baseline in (A-a)DO2 by visit during 24 weeks treatment by Age Group		X					
Table	14.2.1.14	Summary of (A-a)DO2 and change from baseline in (A-a)DO2 by visit during 24 weeks treatment by Sex		X					
Table	14.2.1.15	Summary of (A-a)DO2 and change from baseline in (A-a)DO2 by visit during 24 weeks treatment by aPAP severity		X					
Table	14.2.1.16	Summary of (A-a)DO2 and change from baseline in (A-a)DO2 by visit during 24 weeks treatment by aPAP diagnosis		X					
Table	14.2.1.17	Summary of (A-a)DO2 and change from baseline in (A-a)DO2 by visit during 24 weeks treatment – by strata		X					
Figure	14.2.1.18	Mean profiles of (A-a)DO2 over time by region		X					
Table	14.2.1.19	Summary of (A-a)DO2 and change from baseline in (A-a)DO2 by visit during 24 weeks treatment – by region		X					
Figure	14.2.1.20	Mean profiles of (A-a)DO2 over time by strata		X					
Figure	14.2.1.21	Forest Plot for analyses of change from baseline in (A-a)DO2, Molgramostim OD vs Placebo by subgroups		X					
Figure	14.2.1.22	Forest Plot for analyses of change from baseline in (A-a)DO2, Molgramostim Int. vs Placebo by subgroups		X					
Key Secondary Efficacy Endpoints									
Table	14.2.2.1	Summary of six minutes walking distance (6MWD) and change from baseline in 6MWD by visit during 24 weeks treatment		X	X				
Figure	14.2.2.2	Mean profiles of six minutes walking distance (6MWD) over time		X					
Figure	14.2.2.3	Mean change profiles of six minutes walking distance (6MWD) over time		X					
Table	14.2.2.4	Analysis of change from baseline in six minutes walking distance (6MWD) after 24 weeks (ANCOVA)		X					
Table	14.2.2.5	Sensitivity analysis of change from baseline in six minutes walking distance (6MWD) after 24 weeks (MMRM)		X					
Table	14.2.2.6	Sensitivity analysis of change from baseline in six minutes walking distance (6MWD) after 24 weeks (ANCOVA) – multiple imputation		X					

			SCR	DB-FAS	DB-PPS	DB-SAF	FU-FAS	FU-MOL INT	FU-SAF
Table	14.2.2.7	Sensitivity analysis of change from baseline in six minutes walking distance (6MWD) after 24 weeks (ANCOVA) – completer analysis		X					
Table	14.2.2.8	Sensitivity analysis of change from baseline in six minutes walking distance (6MWD) after 24 weeks (ANCOVA)				X			
Table	14.2.2.9	Summary of six minutes walking distance (6MWD) and change from baseline in 6MWD by visit during 24 weeks treatment by Age Group		X					
Table	14.2.2.10	Summary of six minutes walking distance (6MWD) and change from baseline in 6MWD by visit during 24 weeks treatment by Sex		X					
Table	14.2.2.11	Summary of six minutes walking distance (6MWD) and change from baseline in 6MWD by visit during 24 weeks treatment by aPAP severity		X					
Table	14.2.2.12	Summary of six minutes walking distance (6MWD) and change from baseline in 6MWD by visit during 24 weeks treatment by aPAP diagnosis		X					
Table	14.2.2.13	Summary of six minutes walking distance (6MWD) and change from baseline in 6MWD by visit and strata during 24 weeks treatment		X	X				
Figure	14.2.2.14	Mean profiles of six minutes walking distance (6MWD) over time by strata		X					
Table	14.2.2.15	Summary of six minutes walking distance (6MWD) and change from baseline in 6MWD by visit and region during 24 weeks treatment		X					
Figure	14.2.2.16	Mean profiles of six minutes walking distance (6MWD) over time by region		X					
Figure	14.2.2.17	Forest Plot for analyses of change from baseline in minutes walking distance (6MWD), Molgramostim OD vs Placebo by subgroups		X					
Figure	14.2.2.18	Forest Plot for analyses of change from baseline in minutes walking distance (6MWD), Molgramostim Int. vs Placebo by subgroups		X					
Table	14.2.2.19	Summary of SGRQ total score and change from baseline in SGRQ total score by visit during 24 weeks treatment		X	X				
Figure	14.2.2.20	Mean profiles of SGRQ total score over time		X					
Figure	14.2.2.21	Mean change profiles of SGRQ total score over time		X					
Table	14.2.2.22	Analysis of change from baseline in SGRQ total score after 24 weeks (ANCOVA)		X					
Table	14.2.2.23	Sensitivity analysis of change from baseline SGRQ total score after 24 weeks (MMRM)		X					
Table	14.2.2.24	Sensitivity analysis of change from baseline in SGRQ total score after 24 weeks (ANCOVA) – multiple imputation		X					
Table	14.2.2.25	Sensitivity analysis of change from baseline in SGRQ total score after 24 weeks (ANCOVA) – completer analysis		X					
Table	14.2.2.26	Sensitivity analysis of change from baseline in SGRQ total score after 24 weeks (ANCOVA)				X			
Table	14.2.2.27	Summary of SGRQ total score and change from baseline in SGRQ total score by visit during 24 weeks treatment by Age Group		X					
Table	14.2.2.28	Summary of SGRQ total score and change from baseline in SGRQ total score by visit during 24 weeks treatment by Sex		X					
Table	14.2.2.29	Summary of SGRQ total score and change from baseline in SGRQ total score by visit during 24 weeks treatment by aPAP severity		X					
Table	14.2.2.30	Summary of SGRQ total score and change from baseline in SGRQ total score by visit during 24 weeks treatment by aPAP diagnosis		X					
Table	14.2.2.31	Summary of SGRQ total score and change from baseline in SGRQ total score by visit and strata during 24 weeks treatment		X					
Figure	14.2.2.32	Mean profiles of SGRQ total score over time by strata		X					
Table	14.2.2.33	Summary of SGRQ total score and change from baseline in SGRQ total score by visit and region during 24 weeks treatment		X					
Figure	14.2.2.34	Mean profiles of SGRQ total score over time by region		X					
Figure	14.2.2.35	Forest Plot for analyses of change from baseline in SGRQ total score, Molgramostim OD vs Placebo by subgroups		X					

			SCR	DB-FAS	DB-PPS	DB-SAF	FU-FAS	FU-MOL INT	FU-SAF
Figure	14.2.2.36	Forest Plot for analyses of change from baseline in SGRQ total score, Molgramostim Int. vs Placebo by subgroups		X					
Table	14.2.2.37	Summary of number of subjects in need of WLL during 24-weeks of treatment		X	X				
Table	14.2.2.38	Life table summary of time from randomization to need of WLL		X					
Figure	14.2.2.39	Kaplan – Meier plot for time to need of WLL during 24-weeks of treatment		X					
Table	14.2.2.40	Analysis of difference between treatment groups (logrank test) in time to WLL during 24 weeks of treatment		X					
Table	14.2.2.41	Sensitivity analysis of difference between treatment groups (Cox regression) in time to WLL during 24 weeks of treatment		X					
Table	14.2.2.42	Sensitivity analysis of difference between treatment groups (logrank test) in time to WLL during 24 weeks of treatment – alternative censoring		X					
Table	14.2.2.43	Sensitivity analysis of difference between treatment groups (logrank test) in time to WLL during 24 weeks of treatment			X				
Table	14.2.2.44	Summary of number of subjects in need of WLL during 24-weeks of treatment by Age Group		X					
Table	14.2.2.45	Summary of number of subjects in need of WLL during 24-weeks of treatment by Sex		X					
Table	14.2.2.46	Summary of number of subjects in need of WLL during 24-weeks of treatment by aPAP severity		X					
Table	14.2.2.47	Summary of number of subjects in need of WLL during 24-weeks of treatment by aPAP diagnosis		X					
Table	14.2.2.48	Summary of number of subjects in need of WLL during 24-weeks of treatment by strata and by visit		X					
Figure	14.2.2.49	Kaplan – Meier plot for time to need of WLL during 24-weeks of treatment by strata		X					
Table	14.2.2.50	Summary of number of subjects in need of WLL during 24-weeks of treatment by region		X					
Figure	14.2.2.51	Kaplan – Meier plot for time to need of WLL during 24-weeks of treatment by region		X					
Figure	14.2.2.52	Forest Plot for analyses of time to WLL , Molgramostim OD vs Placebo by subgroups		X					
Figure	14.2.2.53	Forest Plot for analyses of time to WLL, Molgramostim Int. vs Placebo by subgroups		X					
Table	14.2.2.54	Overview of statistical hypothesis testing for primary and key secondary efficacy endpoints according to testing procedure		X					
Further Secondary Efficacy Endpoints									
Table	14.2.3.1	Summary of VC (% predicted) and change from baseline in VC (% predicted) by visit during 24 weeks treatment		X					
Table	14.2.3.2	Analysis of change from baseline in VC (% predicted) after 24 weeks (ANCOVA)		X					
Table	14.2.3.3	Summary of DLCO (% predicted) and change from baseline in DLCO (% predicted) by visit during 24 weeks treatment		X					
Table	14.2.3.4	Analysis of change from baseline in DLCO (% predicted) after 24 weeks (ANCOVA)		X					
Figure	14.2.3.5	Summary of DLCO (% predicted) and change from baseline in DLCO (% predicted) by visit during 24 weeks treatment by aPAP severity		X					
Figure	14.2.3.6	Forest Plot for analyses change from baseline in DLCO (% predicted) by subgroups		X					
Table	14.2.3.7	Summary of FEV1(% predicted) and change from baseline in FEV1(% predicted) by visit during 24 weeks treatment		X					
Table	14.2.3.8	Analysis of change from baseline in FEV1(% predicted) after 24 weeks (ANCOVA)		X					
Table	14.2.3.9	Summary of FVC (% predicted) and change from baseline in FVC (% predicted) by visit during 24 weeks treatment		X					
Table	14.2.3.10	Analysis of change from baseline in FVC (% predicted) after 24 weeks (ANCOVA)		X					
Figure	14.2.3.11	Summary of FVC (% predicted) and change from baseline in FVC (% predicted) by visit during 24 weeks treatment by aPAP severity		X					
Figure	14.2.3.12	Forest Plot for analyses of change from baseline in FVC (% predicted) by subgroups		X					

			SCR	DB-FAS	DB-PPS	DB-SAF	FU-FAS	FU-MOL INT	FU-SAF
Table	14.2.3.13	Summary of PaO2 and relative change from baseline in PaO2 by visit during 24 weeks treatment		X					
Table	14.2.3.14	Analysis of relative change from baseline in PaO2 after 24 weeks (ANCOVA)		X					
Table	14.2.3.15	Number and % of subjects with >5 mmHg/>0.67 kPa improvement in (A-a)DO2 compared to baseline by visit during 24 weeks treatment		X					
Table	14.2.3.16	Analysis of number of subjects with >5 mmHg/>0.67 kPa improvement in (A-a)DO2 compared to baseline after 24 weeks treatment (Logistic regression)		X					
Table	14.2.3.17	Number and % of subjects with >10 mmHg/>1.33 kPa improvement in (A-a)DO2 compared to baseline by visit during 24 weeks treatment		X					
Table	14.2.3.18	Analysis of number subjects with >10 mmHg/>1.33 kPa improvement in (A-a)DO2 compared to baseline after 24 weeks treatment (Logistic regression)		X					
Table	14.2.3.19	Number and % of subjects with >5 percentage points improvement in VC (% predicted) compared to baseline by visit during 24 weeks treatment		X					
Table	14.2.3.20	Analysis of number of subjects with >5 percentage points improvement in VC (% predicted) compared to baseline after 24 weeks treatment (Logistic regression)		X					
Table	14.2.3.21	Number and % of subjects with >10 percentage points improvement in VC (% predicted) compared to baseline by visit during 24 weeks treatment		X					
Table	14.2.3.22	Analysis of number of subjects with >10 percentage points improvement in VC (% predicted) compared to baseline after 24 weeks treatment (Logistic regression)		X					
Table	14.2.3.23	Number and % of subjects with >10 percentage points improvement in DLCO (% predicted) compared to baseline by visit during 24 weeks treatment		X					
Table	14.2.3.24	Analysis of number of subjects with >10 percentage points improvement in DLCO (% predicted) compared to baseline after 24 weeks treatment (Logistic regression)		X					
Table	14.2.3.25	Number and % of subjects with >10 percentage points improvement in FEV1(% predicted) compared to baseline by visit during 24 weeks treatment		X					
Table	14.2.3.26	Analysis of number of subjects with >10 percentage points improvement in FEV1(% predicted) compared to baseline after 24 weeks treatment (Logistic regression)		X					
Table	14.2.3.27	Number and % of subjects with >10 percentage points improvement in FVC (% predicted) compared to baseline by visit during 24 weeks treatment		X					
Table	14.2.3.28	Analysis of number of subjects with >10 percentage points improvement in FVC (% predicted) compared to baseline after 24 weeks treatment (Logistic regression)		X					
Table	14.2.3.29	Number and % of subjects with >10% relative improvement in PaO2 compared to baseline by visit during 24 weeks treatment		X					
Table	14.2.3.30	Analysis of number of subjects with >10% relative improvement in PaO2 compared to baseline after 24 weeks treatment (Logistic regression)		X					
Table	14.2.3.31	Summary of change from baseline in SpO2 at start and the worst SpO2 oxygen desaturation and distance of walk during 6 minutes walk test (6MWT) by visit during 24 weeks treatment		X					

			SCR	DB-FAS	DB-PPS	DB-SAF	FU-FAS	FU-MOL INT	FU-SAF
Table	14.2.3.32	Number of subjects with improved tolerance to exercise (increase from baseline in distance walked ≥ 50 m) by visit during 24 weeks treatment		X					
Table	14.2.3.33	Analysis of number of subjects with improved tolerance to exercise (increase from baseline in distance walked ≥ 50 m) after 24 weeks treatment (Logistic regression)		X					
Table	14.2.3.34	Number of subjects with improved tolerance to exercise (desaturation < 4 percentage points on the 6MWT) by visit during 24 weeks treatment full analysis set		X					
Table	14.2.3.35	Analysis of number of subjects with improved tolerance to exercise (desaturation < 4 percentage points on the 6MWT) after 24 weeks treatment (Logistic regression)		X					
Table	14.2.3.36	Summary of Borg CR10 pre post and corresponding difference in walk dyspnea score and change from baseline in scores by visit during 24 weeks treatment		X					
Table	14.2.3.37	Analysis of change from baseline in dyspnea score after 24 weeks (ANCOVA)		X					
Table	14.2.3.38	Summary of cough (VAS) scores and change from baseline in cough scores by visit during 24 weeks treatment		X					
Table	14.2.3.39	Analysis of change from baseline in cough (VAS) scores after 24 weeks (ANCOVA)		X					
Table	14.2.3.40	Summary of number of subjects with Improved Worsened or No change in CT score during 24 weeks of treatment		X					
Table	14.2.3.41	Summary of CT Ground-Glass Opacification (GGO) score during 24 weeks of treatment		X					
Table	14.2.3.42	Analysis of number of subjects with Improved CT score compared to baseline after 24 weeks treatment (Logistic regression)		X					
Table	14.2.3.43	Summary of number of WLLs over time		X					
Table	14.2.3.44	Summary of details related to WLLs including reasons for, one or both lungs, and saline volume used.		X					
Table	14.2.3.45	Analysis of number of WLLs over time (negative binomial regression)		X					
Exploratory Efficacy Endpoints Double-Blind Treatment Period									
Table	14.2.4.1	Summary of time during which the (A-a)DO ₂ level is maintained below baseline (A-a)DO ₂ level -10 mmHg		X					
Table	14.2.4.2	Summary of time period during which the improvement in tolerance to exercise is maintained		X					
Table	14.2.4.3	Summary of SGRQ dimension scores and corresponding changes from baseline by visit during 24 weeks of treatment		X					
Table	14.2.4.4	Summary of number of subject with improved QoL score (improvement of at least 4 units on SGRQ total score) during 24 weeks of treatment		X					
Table	14.2.4.5	Summary of EQ-5D-5L dimension scores and corresponding shifts from baseline by visit during 24 weeks of treatment		X					
Table	14.2.4.6	Summary of Krebs von den Lungen-6 (KL-6) and change from baseline in Krebs von den Lungen-6 (KL-6) by visit during 24 weeks of treatment		X					
